***Design***

Patients who voluntarily agreed to participate in the study were randomly assigned into two groups. Patients enrolled in the study were referred for an initial consultation with a dietitian following their diagnosis by a gastroenterologist. The energy-restricted diet group followed an energy-restricted diet for 8 weeks, while the energy + time-restricted diet group followed the same diet and a 16:8 eating pattern and restricted food intake to an 8 h window each day. The effectiveness of the intervention was assessed using anthropometric and biochemical measurements, and Fibroscan investigations were performed before the intervention (T0) and after the intervention (T8).

***Measurements***

Blood samples were collected from patients after 12 h of fasting. The samples were centrifuged for 15 min and stored at -80 °C after serum separation until analysis. Serum FGF-21, Beclin-1, and ATG-5 were analyzed using enzyme-linked

immunosorbent assay (ELISA) kits, following the manufacturer's protocols (Human FGF-21 ELISA, Biovendor, Brno, Czech Republic; Human BECN1 [Beclin-1] ELISA Kit, ElabScience, Houston, TX, USA; Human Autophagy protein 5 [ATG5] ELISA Kit, MyBioSource, Inc., San Diego, USA) and in duplicate.

- The extent of hepatic steatosis and fibrosis was determined using transient elastography on a Fibroscan 502 TouchR device(Echosens SA, Paris, France). All Fibroscan measurements were performed following the manufacturer's instructions as specified previously.
- Patients' heights were measured using a stadiometer (Seca 769), barefoot, feet side by side, and head in the Frankfort plane. Body composition was determined using the bioelectrical impedance method (Tanita MC 780 P).

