Official Title of the study: Effects of Intermittent Fasting in Metabolic Dysfunction Associated Fatty Liver Disease

NCT number: NCT06664684

Date of the document: 06.05.2022

Statistical Analysis Plan

Study data were analyzed using SPSS 28.0 software suit. Statistical significance was set at $p < 0.05$ for all analyses. Data were checked for normality of distribution using the Kolmogorov–Smirnov test. Categorical variables were analyzed using the chi-square test. Median (Quartile 1–Quartile 3) values were used in descriptive statistics. The Mann–Whitney U test was used to determine whether the baseline values were similar between the two groups before the intervention. The before/after comparison of the quantitative data was performed using the Wilcoxon test.

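### Could hours since the last meal differ between the arms when blood is drawn at T8?

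*Protocol*

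**What the plan says.** The Protocol (Measurements) has one sentence on preparation for sampling: "Blood samples were collected from patients after 12 h of fasting". It does not label 12 h as exact or as a minimum, and it gives no clock times. The same section names the markers: "Serum FGF-21, Beclin-1, and ATG-5 were analyzed using enzyme-linked" immunosorbent assay.

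The Protocol (Design) puts both arms on the same energy restriction for 8 weeks. The energy + time-restricted arm "followed the same diet and a 16:8 eating pattern and restricted food intake to an 8 h window each day". No eating window is stated for the energy-restricted arm, and the clock position of the 8 h window is not given. Assessments are at T0 and T8.

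The SAP does not mention fasting hours. Its Mann–Whitney U test is "used to determine whether the baseline values were similar between the two groups before the intervention". For change over time it says: "The before/after comparison of the quantitative data was performed using the Wilcoxon test".

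**The concern.** In most trials a loosely described overnight fast adds noise that both arms share. Here the daily fasting pattern is the only stated difference between the arms, so the concern deserves a check.

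If 12 h was only a floor, a patient on 16:8 could arrive at T8 well past it because of the assigned arm. Randomisation would not balance this, since assignment would be its cause. The difference would fall on the between-arm contrast, which is the only contrast that can separate the eating pattern from the shared diet. If the markers move with hours since eating, an effect of 8 weeks of time restriction could not be told apart from one longer fast before the draw. Neither SAP test for quantitative data takes account of those hours.

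**Working it through.** **Inputs from the documents.** Pre-sampling fast 12 h (Protocol, Measurements). Eating window 8 h in one arm only (Protocol, Design). The plan gives no other figure on fasting hours, so there is none to reproduce.

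**Inputs not in the documents, assumed below.** Draw time, window closing time, spread of fasting hours in each arm, slope of the markers on fasting hours, and number of patients.

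**Step 1: implied daily fast.** 24 − 8 = 16 h, which exceeds the stated figure by 16 − 12 = 4 h.

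**Step 2: clock check.** Hours fasted at the draw = 24 − closing time + draw time. With an assumed 08:00 draw:

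| Window closes | Hours at 08:00 | Clock time of hour 12 |
|---|---|---|
| 20:00 | 24 − 20 + 8 = 12 | 08:00 |
| 18:00 | 24 − 18 + 8 = 14 | 06:00 |
| 16:00 | 24 − 16 + 8 = 16 | 04:00 |

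A 12 h fast is therefore compatible with 16:8. A window closing at 20:00 gives exactly 12 h at 08:00. An early-closing window makes 12 h awkward to achieve, but the documents do not say that early windows were used.

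**Step 3: difference in hours under each reading.** If 12 h is exact for everyone, the difference is 0 h. Otherwise, suppose time-restricted draws at T8 spread evenly over 12 to 16 h (mean 14 h), and the reference (comparator at T8, and both arms at T0) spreads evenly over 12 to 12 + r h. Then:

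- mean difference = 14 − (12 + r/2) = 2 − r/2
- share of pairs with the longer fast in the time-restricted arm = 1 − r/8
- shift in the arm contrast at an assumed slope of 0.10 SD of change per hour = 0.10 × (2 − r/2)

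| Reference hours | Range of difference | Mean | Share longer | Shift |
|---|---|---|---|---|
| exactly 12 (r = 0) | 0 to +4 h | 2.0 h | 100% | 0.20 SD |
| 12–13 (r = 1) | −1 to +4 h | 1.5 h | 87.5% | 0.15 SD |
| 12–14 (r = 2) | −2 to +4 h | 1.0 h | 75% | 0.10 SD |
| 12–16 (r = 4) | −4 to +4 h | 0 h | 50% | 0 SD |

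The top row treats the same sentence as exact for one group and as a floor for the other. The bottom row treats it as a floor for both with the same spread, and the mean difference vanishes. The middle rows need a view of comparator eating habits that the documents do not supply.

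**Step 4: what this would do to a test.** With no true arm difference, the 0.10 SD slope, and an assumed 20 or 30 patients per arm, 20,000 simulated trials put the rate of p < 0.05 for a Mann–Whitney test on change at 8.6% and 10.9% (r = 0), 6.0% and 6.4% (r = 2), and 5.0% and 4.8% (r = 4). The SAP states no between-arm test of change. For the within-arm Wilcoxon test that it does state, with r = 2, the rate is 6.6% (20 patients) and 8.1% (30 patients) at the same slope.

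**The case for a change.** The strongest case for acting is this. Fasting time is bound up with what is randomised, so it should not be left to interpretation in the one place where it could bias the key contrast. That a harmless reading exists does not show that it applied. Meeting both 12 h and an early-closing window would mean a draw at 06:00 or 04:00, which makes some drift past 12 h plausible. Clarifying costs almost nothing.

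Part of this stands. The text does not label 12 h as fixed or minimum, and does not say whether last-intake and draw times were recorded. A reader interested in the blood markers would reasonably want to know.

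The step from there to a bias does not stand. It requires all of the following:

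- 12 h was a minimum
- 16:8 was kept up to the T8 draw
- the window closed early relative to the draw
- comparator patients fasted for less time
- the markers move between hours 12 and 16

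The documents state none of these. Nor is the SAP's silence a defect that can usefully be repaired in the analysis: if fasting hours did differ because of arm, they would be a consequence of assignment, and adjusting for them would be exploratory at most. The lack of any stated between-arm test of change is a separate matter and does not make this one larger. The point also touches blood measures only, since the 12 h rule is attached to blood samples and not to Fibroscan or body composition.

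**Conclusion.** The concern does not call for a change. The Protocol sets one interval for all patients, and on its ordinary reading the arms are sampled at the same number of hours, so the difference is 0 h. If 12 h is a minimum in both arms with similar spread, the mean difference is also 0 h. A mean gap of 1 to 2 h, and a shift of 0.1 to 0.2 SD in the arm contrast, arises only with asymmetric fasting hours and a slope that are both assumed. The documents do not allow the size or sign of any marker effect to be determined, and nothing in them shows that hours did differ.

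What remains is a detail that analysts and authors can supply when reporting: whether 12 h was fixed or a minimum and, if times were recorded, the hours by arm and visit in the SAP's median and quartile format. If no times exist, a limitation sentence for the blood markers covers it. This conclusion rests on reading the sentence in the same way for both arms and both visits. Evidence that 12 h was applied differently by arm would reopen the question.

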**Official Title of the study: Effects of Intermittent Fasting in Metabolic Dysfunction Associated Fatty Liver Disease**

**NCT number: NCT06664684**

**Date of the document: 06.05.2022**

**Study Protocol**

***Patients***

This study was approved by the Ethics Committee of Marmara University School of Medicine (No: 09.2022.707) Informed consent was obtained from each patient included in the study. This is a prospective non-drug intervention study conducted by the same gastroenterologist on patients diagnosed with MAFLD. Individuals with fatty liver disease diagnosed by vibration-controlled transient elastography are diagnosed with MAFLD if at least one of the following three conditions is present: overweight/obesity, type 2 diabetes mellitus (T2DM), or underweight or normal weight with at least two metabolic risk abnormalities [waist circumference, blood pressure, triglycerides, high-density lipoprotein cholesterol (HDL-C), prediabetes, insulin resistance, high-sensitivity C reactive protein (CRP)]. All of our patients were diagnosed with MAFLD because their BMI was above 25 kg/m^2 in addition to the detection of fatty liver.

Exclusion criteria were patients with an average daily alcohol consumption of >20 g for females and >30 g for males; pregnant or lactating women; patients with ischemic heart disease or heart failure, chronic inflammatory diseases, chronic viral infections, cancer, moderate-to-severe kidney disease, uncontrolled hypertension, and eating disorders; those with a history of bariatric surgery; and those on insulin due to increased risk of hypoglycemia.

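### The plan labels an elastography reading taken 8 weeks apart as fibrosis, but nothing in the plan justifies reading a change, or no change, in it as a statement about fibrosis

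*Protocol*

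**What the plan says.** **What the scan is said to measure.** Protocol, Measurements: "The extent of hepatic steatosis and fibrosis was determined using transient elastography on a Fibroscan 502 TouchR device". The documents describe no biopsy, serum fibrosis marker or other measure that could confirm the reading.

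**When it is taken.** Protocol, Design: "The energy-restricted diet group followed an energy-restricted diet for 8 weeks", and the other group follows the same diet with a 16:8 eating pattern. The same section says that "Fibroscan investigations were performed before the intervention (T0) and after the intervention (T8". No later visit is described.

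**What role it has.** The sentence that schedules the scan opens with "The effectiveness of the intervention was assessed using anthropometric and biochemical measurements" and then turns to Fibroscan. Its use as a measure of effectiveness is implied. No primary or secondary endpoint is named.

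**Who enters.** Protocol, Patients: "Individuals with fatty liver disease diagnosed by vibration-controlled transient elastography are diagnosed with MAFLD if at least one of the following three conditions is present". All participants qualified through a BMI above 25 kg/m², "in addition to the detection of fatty liver". No minimum stiffness or fibrosis stage is set.

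**How it is analysed.** The SAP compares quantitative measures before and after with the Wilcoxon test and uses the Mann-Whitney U test for baseline values only. The significance level is 0.05 throughout. The SAP does not mention Fibroscan, fibrosis, or how any single outcome is to be interpreted.

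**The concern.** The same scan yields a reading for fat and a reading that the protocol calls fibrosis. Once the second carries that name, is repeated after the intervention and is tested for change, the plan leaves two statements open to whoever reports the trial: that fibrosis improved if the reading falls significantly, and that the diets had no effect on fibrosis if it does not. Both need support that the plan does not supply.

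A fall would need evidence that the reading moved because fibrosis moved. A flat result would need evidence that participants had fibrosis able to improve and that 8 weeks was long enough to show it. At stake is the wording of a conclusion, not patient safety or the conduct of the randomisation. But a claim about fibrosis in fatty liver disease is one that readers would take seriously.

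**Working it through.** There is no figure to reproduce. The documents give no sample size, power, effect size, standard deviation or cut-off for the reading. The check sets the sections side by side.

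1. **Is the reading labelled fibrosis?** Yes, in Measurements. The word stiffness appears nowhere in either document.

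2. **Is it repeated after the intervention?** Yes, in Design, at T0 and T8 only. The interval is the 8 weeks of the diet.

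3. **Is it tested for change?** By implication. The SAP's Wilcoxon test covers quantitative data with no exception stated, so a continuous reading falls under it. The SAP does not say whether the result will be kept as a value or as a stage, or whether the test is run within each arm.

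4. **Does entry ensure fibrosis at T0?** No. Patients lists fatty liver plus a metabolic condition, and every participant met it through BMI. A person with a normal reading is eligible. The documents do not say how many such people were enrolled.

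5. **Is there a second measure to confirm a fibrosis change?** None is described.

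6. **Could the planned tests attribute a change to the eating pattern?** No. Participants were "randomly assigned into two groups", and both groups follow the energy-restricted diet. The only between-group test of quantitative data is on baseline values. A before/after fall in either group could reflect energy restriction, time or measurement variation.

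Taking the possible results in turn:

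| Result at T8 | Fibrosis reading | Why the plan does not settle it |
|---|---|---|
| Reading falls | Fibrosis improved | One indirect measure with nothing to confirm it (steps 1, 5). Under the assumption below, less fat or inflammation would also lower it |
| Reading unchanged | No effect on fibrosis | No fibrosis needed at entry (step 4). Only 8 weeks observed (step 2). Precision unknown because no sample size is stated |

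**Assumption.** That fibrosis changes slowly, and that the device measures stiffness, which can also move with liver fat or inflammation, is general clinical background. Neither document says so. Without it, steps 1 to 5 still show one indirect reading, no confirming measure, no fibrosis criterion at entry and no rule of interpretation.

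**The case against.** **Fibrosis is not a named effectiveness outcome.** This is correct. Design ties effectiveness explicitly to anthropometric and biochemical measures, and Fibroscan follows in the same sentence. The device is also the diagnostic tool, so the fibrosis reading may serve partly as baseline description. A reader might infer that the plan commits the sponsor to reporting a stiffness fall as improved fibrosis. It does not: no fibrosis hypothesis, cut-off or intended claim appears. What stands is narrower. The T8 scan has no other stated purpose, its second reading is called fibrosis, and nothing restrains the inference.

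**The argument borrows clinical facts.** This is partly right, which is why they are labelled as an assumption. They strengthen the point but do not carry all of it.

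**Participants may have fibrosis.** They may. A reader might infer from the entry criteria that they have none and so no room to improve. The documents do not support that either, since the absence of a criterion says nothing about baseline values.

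**The dilution can be quantified.** It is tempting to assume that only some share of participants can improve and to scale the average effect by that share. The documents give no such share. The model also conflicts with the assumption above: if stiffness falls with fat or inflammation, participants without fibrosis could show a fall too. A diluted mean is also not what a rank-based test examines. No such figure is offered here.

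**The missing between-arm test is the larger defect.** It is at least as important, and it affects the steatosis reading too. Relabelling does not cure it, so the steatosis result should not be taken as free of difficulty.

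**Conclusion.** The point holds as a limit on inference. The plan gives the name fibrosis to one indirect reading, takes it twice around an 8-week diet, and exposes it to a significance test. It has no fibrosis requirement at entry and no confirming measure. It therefore does not justify turning a change, or no change, in that reading into a conclusion about fibrosis.

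A reader might go further and say that an 8-week change can never support a fibrosis conclusion in either direction. That is too absolute. It would need facts on the time course of fibrosis and on other causes of stiffness change, which the documents do not contain.

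No numerical size can be attached. The practical weight is modest: data collection and randomisation are untouched, and what changes is what the trial may claim. The verdict rests on reading Fibroscan as an implied effectiveness measure and, for the alternative explanations of a fall, on the stated background assumption.

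**What to change.** In the protocol and SAP:

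1. Call the second Fibroscan reading *liver stiffness*, and list it as exploratory.
2. Report its baseline distribution by arm, so that readers can see how much room for change there was.
3. State that no conclusion about improvement in fibrosis, or lack of it, will be drawn from T0-T8.
4. If change in stiffness is compared at all, compare it between the randomised arms, with an estimate and interval. Do not rely on before/after tests.

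Suggested text: *Liver stiffness by transient elastography is an exploratory measure. Its baseline distribution will be reported by arm. Any comparison of change from T0 to T8 will be between the randomised arms. No inference about fibrosis will be made from it.*

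Do not add a before/after analysis split by raised stiffness at T0. People selected for a high reading tend to read lower on repeat even with no true effect (regression to the mean), and the documents give no threshold for raised.

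**Cost.** A few sentences, one descriptive table and, if change is compared, one added between-arm analysis. All of it uses data that the plan already collects, with no new visit or participant. The price is that the sponsor gives up a fibrosis claim at 8 weeks.

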Official Title of the study: Effects of Intermittent Fasting in Metabolic Dysfunction Associated Fatty Liver Disease

NCT number: NCT06664684

Date of the document: 06.05.2022

Statistical Analysis Plan

Study data were analyzed using SPSS 28.0 software suit. Statistical significance was set at $p < 0.05$ for all analyses. Data were checked for normality of distribution using the Kolmogorov–Smirnov test. Categorical variables were analyzed using the chi-square test. Median (Quartile 1–Quartile 3) values were used in descriptive statistics. The Mann–Whitney U test was used to determine whether the baseline values were similar between the two groups before the intervention. The before/after comparison of the quantitative data was performed using the Wilcoxon test.

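### Six or more outcomes are each tested at p < 0.05 with no primary outcome, testing order, multiplicity adjustment or success rule; if any one significant result counts as effectiveness, the error rate exceeds 5%

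*SAP*

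**What the plan says.** The SAP, a single paragraph, sets the same threshold for every test: "Statistical significance was set at $p < 0.05$ for all analyses". It assigns the Wilcoxon test to before/after comparisons of the quantitative data in general. Mann–Whitney is assigned to the comparison of the two groups at baseline only.

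The protocol's Design section describes a randomised comparison: "Patients who voluntarily agreed to participate in the study were randomly assigned into two groups". Both arms receive the same energy restriction, and one adds a 16:8 eating window: "The energy-restricted diet group followed an energy-restricted diet for 8 weeks, while the energy + time-restricted diet group followed the same diet". Success is described by classes of measurement, with none ranked first: "The effectiveness of the intervention was assessed using anthropometric and biochemical measurements, and Fibroscan investigations", taken at T0 and T8.

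The Measurements section identifies the variables:

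- "Serum FGF-21, Beclin-1, and ATG-5 were analyzed using enzyme-linked" (three serum markers)
- "The extent of hepatic steatosis and fibrosis was determined using transient elastography" (two Fibroscan measures)
- "Body composition was determined using the bioelectrical impedance method" (at least one variable; the individual ones are not listed)

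Neither document names a primary or secondary outcome, a testing order, an adjustment for multiple testing, or the number of significant results that would count as effectiveness.

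**The concern.** With a full 5% on each outcome and no success rule, the plan leaves open a claim of effectiveness based on whichever outcome reaches p < 0.05. Under that reading, the chance of a false claim is well above 5%. If every outcome had to be significant, it would not be. The plan does not say which reading applies, so a reader cannot tell what error rate stands behind a positive result.

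Adjusting the before/after tests alone would not repair this. Both arms follow the same energy-restricted diet, so a change from T0 to T8 may reflect the shared diet, time in the study or regression to the mean. The randomised question is whether time restriction adds anything, and that is answered by comparing the arms. The error rate therefore needs to be controlled on between-arm comparisons, and the SAP states none after baseline.

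**Working it through.** **Inputs from the documents.** Threshold per test: 0.05 (SAP). Outcomes: 3 serum markers + 2 Fibroscan measures + 1 for body composition = 6 (protocol, Measurements). Six is a minimum. Treating these measurements as effectiveness outcomes is an inference from matching them to the classes named in the Design section.

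**Assumptions.** Tests are two-sided (the SAP does not state sidedness). The documents give no correlations between outcomes, so a range is shown. The plan states no overall error rate, so there is no figure to reproduce; one test at 0.05 has error 0.05.

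**Any one of six significant, all nulls true.** For independent tests the error is 1 − (1 − 0.05)^k:

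- k = 6: 1 − 0.95^6 = 0.265
- Upper bound under any correlation: 6 × 0.05 = 0.30

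For equally correlated normal test statistics with correlation ρ and c = 1.96, the error is

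1 − ∫ φ(u) [Φ((c − √ρ·u)/√(1 − ρ)) − Φ((−c − √ρ·u)/√(1 − ρ))]^k du,

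evaluated by numerical integration:

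| ρ | Error, k = 6 |
|---|---|
| 0 | 0.265 |
| 0.3 | 0.241 |
| 0.5 | 0.207 |
| 0.8 | 0.139 |

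These values describe six between-arm tests when time restriction adds nothing. If all six had to be significant, the error would be at most 0.05.

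**The before/after tests the SAP does state.** Six true nulls are doubtful here because both arms diet. As an illustration, suppose only three outcomes are truly unchanged:

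- One test per outcome: 1 − 0.95^3 = 0.143 if independent; 0.098 at ρ = 0.8.
- One test per outcome in each arm, arms independent: 1 − 0.95^6 = 0.265 if independent; 1 − (1 − 0.098)^2 = 0.186 at within-arm ρ = 0.8.

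The SAP does not say whether the tests are pooled or run by arm.

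**Proposed remedy: primary at 0.05, then Holm on five secondaries only if the primary is significant.**

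- All six nulls true: any rejection requires the primary to be rejected, so the error is 0.050 whatever the correlation. Simulation with 1,000,000 draws gave 0.050 at ρ = 0, 0.3, 0.5 and 0.8.
- Primary effect real and always detected, five null secondaries: 0.049, 0.047, 0.042 and 0.030 at the same four correlations.
- Without the gate, all nulls true: 1 − 0.95 × 0.99^5 = 0.0966 at ρ = 0, falling to 0.062 at ρ = 0.8. The gate is therefore needed.

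**Fallback: one Holm family of six.** All-null error is 0.049, 0.046, 0.041 and 0.028 at the same four correlations.

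**Holm first-step thresholds.** 0.05/5 = 0.0100 for five secondaries; 0.05/6 = 0.0083 for a family of six.

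**The case against.** The strongest reply is that the inflation is conditional. The protocol assesses effectiveness with groups of measurements and never says that one significant result is enough, so what is shown is an unstated rule. That is correct, and it limits the claim. The gap still matters, because a plan that fixes neither the rule nor the primary outcome permits the most lenient reading.

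A second reply is that the 14% to 26% range belongs to between-arm tests the SAP does not contain. This also stands. For the stated Wilcoxon tests, the three-unchanged-outcomes illustration is more relevant. Its choice of three is arbitrary, and its 10% to 14% assumes one test per outcome; testing each arm separately would raise it to between 19% and 26%.

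Third, the missing between-arm test could be seen as a separate defect. It overlaps with this one, but a multiplicity fix confined to before/after tests would control error on a question that cannot isolate time restriction.

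Fourth, the study might be meant as exploratory. Neither document says so. If that is the intention, stating it and making no confirmatory claim would be a legitimate alternative.

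Finally, a primary outcome may be named somewhere outside these two documents. The point here is only that neither the protocol nor the SAP names one.

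**Conclusion.** The concern holds. Within these two documents, at least six unranked outcomes share an unadjusted 0.05 threshold with no success rule. If any one significant outcome is taken as effectiveness and time restriction adds nothing, the false-positive rate over six between-arm tests is 26% under independence and 14% at correlation 0.8. Every correlation examined gives a value above 5%. The size depends on the any-one rule, two-sided testing, the assumed correlations and a count of six, which is a minimum; more variables would generally raise it. This should be corrected. Confidence is medium because the success rule, the number of variables and the use of the before/after tests by arm are all unstated.

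**What to change.** In the SAP:

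1. Name one primary outcome, for example the Fibroscan steatosis reading. Define it as a between-arm comparison of T0-to-T8 change, or of T8 adjusted for T0. State which, name the test, and use two-sided 0.05.
2. Test the other between-arm outcomes with Holm adjustment only if the primary is significant; otherwise report them as exploratory. List the variables, including each body composition variable, so that the family is fixed.
3. Report the before/after Wilcoxon tests as descriptive.
4. If the data have already been seen (the SAP is written in the past tense, which does not settle the matter), label any choice of primary as post hoc. Instead, report all between-arm outcomes measured at T0 and T8 in one Holm-adjusted family. Holm does not correct for choosing the form of the comparison after seeing the data, so that choice should be disclosed too.

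The cost is SAP wording and a between-arm analysis of the T0 and T8 measurements the protocol already provides for; nothing new is measured. No secondary can carry a confirmatory claim if the primary is not significant, and thresholds tighten: Holm's first step is 0.05 divided by the number of secondary variables actually tested, or by all variables in the single-family fallback. With more body composition variables these fall below 0.010 and 0.0083. The loss of power cannot be quantified because neither document gives a sample size.

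### The SAP plans no estimate or confidence interval for the per-patient T8-T0 change in quantitative outcomes, either within or between the randomised arms

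*SAP*

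**What the plan says.** The SAP is one paragraph. For quantitative data it names four things:

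- A summary: "Median (Quartile 1–Quartile 3) values were used in descriptive statistics".
- A test of change: "The before/after comparison of the quantitative data was performed using the Wilcoxon test". It does not say whether this is run in each arm or pooled. I read it as the signed-rank test, run within each arm.
- A between-group test, for baseline only: "The Mann–Whitney U test was used to determine whether the baseline values were similar between the two groups before the intervention".
- A distribution check with no stated consequence: "Data were checked for normality of distribution using the Kolmogorov–Smirnov test".

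The threshold is common to everything: "Statistical significance was set at $p < 0.05$ for all analyses". The SAP names no per-patient change, effect size, confidence interval, transformation or analysis scale.

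The Protocol's Design section says: "Patients who voluntarily agreed to participate in the study were randomly assigned into two groups". Both groups follow the same energy-restricted diet, and one adds the 8-hour eating window. Outcomes are measured at T0 and T8. The Measurements section lists three serum markers by ELISA, FGF-21, Beclin-1 and ATG-5, and says nothing about their distribution.

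**The concern.** The signed-rank test works on each patient's T8-T0 difference, and nothing in the planned reporting describes that difference. A reader who wants the size of the change must subtract one group median from another. That ignores the pairing and comes with no interval.

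The between-arm gap is more serious. Both arms receive the diet, so both may improve, and the randomised question is how much the eating window adds. The plan has no estimate or test of that quantity for quantitative outcomes. What remains is to compare two within-arm p-values, which does not test the difference between arms.

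A smaller matter is the scale. A signed-rank test on raw differences and one on log ratios can give different p-values. The SAP does not say which it uses, and it attaches no action to the normality check that might have decided it.

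**Working it through.** **Inputs.** From the documents: T0 and T8, two randomised groups, significance level 0.05 (sidedness not stated; two-sided assumed). The documents give no sample size, SD, correlation, effect size or power, so there is no figure of the plan's own to reproduce. Assumed: 20 to 30 patients per arm, T0-T8 correlation ρ of 0.5 to 0.9, and either normal data or lognormal data with a T8/T0 ratio of 0.75.

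**Step 1: three candidate numbers for the change.** In one large simulated lognormal example (baseline median 1, baseline log-SD 0.8, SD of log change 0.5, ratio 0.75):

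- difference of the two medians: -0.249
- median of the paired differences: -0.199
- Hodges–Lehmann estimate (median of all pairwise averages of the differences, the quantity that goes with the signed-rank test): -0.252

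The first and third nearly agree here, so the main objection to subtracting medians is noise and the missing interval rather than bias.

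**Step 2: how much noisier, in large samples.** For bivariate normal data with common SD σ:

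- Var(difference of medians) ≈ (2σ²/n)(π/2 − arcsin ρ) = (2σ²/n) arccos ρ
- Var(Hodges–Lehmann change) ≈ (2σ²/n)(1 − ρ)(π/3)
- Ratio = 3 arccos ρ / [π(1 − ρ)]

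With the numbers in:

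- ρ = 0.5: 3 × 1.047 / (3.142 × 0.5) = 2.0
- ρ = 0.7: 3 × 0.795 / (3.142 × 0.3) = 2.5
- ρ = 0.9: 3 × 0.451 / (3.142 × 0.1) = 4.3

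**Step 3: the same ratio by simulation, n = 20 to 30.**

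| ρ | Normal data | Lognormal, log-SD 0.8 |
|---|---|---|
| 0.5 | 1.8–2.0 | about 1.4–1.5 |
| 0.7 | 2.1–2.4 | about 1.7 |
| 0.9 | 3.1–3.9 | about 2.1–2.2 |

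At log-SD 1.0 and ρ = 0.5 the ratio is 1.3 to 1.4. The overall ranges are therefore about 1.8 to 3.9 (normal) and 1.3 to 2.2 (lognormal). As standard errors these are √1.8 = 1.34 to √3.9 = 1.97, and √1.3 = 1.14 to √2.2 = 1.48.

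**Step 4: why two within-arm p-values cannot stand in for a contrast.** Suppose a marker truly falls by the same 25% in both arms (log-SD 0.8, ρ = 0.7). Simulated raw-scale signed-rank power is 0.426 at n = 20 and 0.607 at n = 30. The chance that exactly one arm is significant is 2 × power × (1 − power):

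- n = 20: 2 × 0.426 × 0.574 = 0.49
- n = 30: 2 × 0.607 × 0.393 = 0.48

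So about half of such trials would look as if the arms differ when they do not.

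**Step 5: does the scale matter for the planned test?** Signed-rank power, raw against log:

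| Model of change | n = 20 | n = 30 |
|---|---|---|
| Proportional, 25% fall, log-SD 0.8, ρ 0.7 | 43% vs 48% | 61% vs 67% |
| Proportional, 25% fall, log-SD 0.5, ρ 0.7 | 84% vs 86% | 95% vs 97% |
| Additive, baseline median 10, log-SD 0.8, change N(-0.5, 1) | 54% vs 51% | 73% vs 70% |

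In the first row the two scales disagree on significance in 12 to 13% of trials. In the second they disagree in about 5% (n = 20) and 2% (n = 30). Across a wider set of proportional models with SD of log change 0.5, log gained about 2 to 10 points. In the additive model of the third row, with log-SD 0.5 to 1.0, it lost 0 to 5.5. In a second additive set-up, with larger changes and a floor near zero, log was about equal or up to about 6 points better. Type I error stayed at about 4 to 5.5% on both scales.

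**The case against.** The strongest reply is that this is a reporting refinement. The signed-rank test is valid, medians with quartiles are a respectable summary, and with no transformation named the natural reading is raw data. The variance ratios near 4 belong to highly correlated normal data; for skewed markers the penalty is roughly half that. All of this stands, and it limits the size of the within-arm point. It does not answer the absence of any interval, or of any between-arm estimate.

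A reader might go further and infer that the ELISA markers are right-skewed and therefore lose power on the raw scale, so that log analysis should be mandatory. The documents do not support that. They report no skewness, and skewness alone does not cause a loss: the change must also be roughly proportional to level. In the additive model tabulated above, the log scale does worse.

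A reader might also quote the larger between-arm power gaps that simulation can produce between raw and log change. Those describe a test the SAP does not contain, so they cannot be counted as a loss under this plan. The unused normality check changes no result, and its presence is harmless.

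**Conclusion.** The point holds as an omission, and the documents do not contradict themselves. For quantitative outcomes the SAP gives no estimate or interval for the per-patient change and no between-arm estimate of change, despite randomisation. Both follow from the text alone and need no assumption about distributions. The finding is confined to quantitative outcomes, because the SAP does not say at which time points its chi-square test is applied.

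The size of the noise penalty, about 1.8 to 3.9 times the variance (normal) or 1.3 to 2.2 times (lognormal, log-SD about 0.8 to 1.0), rests on the assumed sample size and correlations. The effect of scale on within-arm power is a few points in either direction, depending on how the markers change. It justifies stating the scale but not imposing one. The validity of the planned test is not in question. The change is worth making mainly because, without the between-arm estimate, the trial cannot say how much the eating window adds.

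**What to change.** Amend the SAP as follows.

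1. For each quantitative outcome, report the per-patient T8-T0 change in each arm as a Hodges–Lehmann estimate with a 95% CI, beside the T0 and T8 medians with quartiles.
2. Report the between-arm difference in change as a Hodges–Lehmann shift with a 95% CI and its Mann–Whitney p-value. State that comparative conclusions rest on this, and not on comparing the within-arm p-values.
3. State, before the analysis is run, the scale used for FGF-21, Beclin-1 and ATG-5. A log ratio reported as percentage change is an option if proportional change is expected. It needs positive values, so it also needs a rule for results below the assay limit.

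The cost is a few sentences of SAP text and a little extra analysis of data already collected. No new patients, visits or assays are needed.
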